
9.5 Missing Data

Baseline data, except for spirometry measurements, are expected to have few or no missing values. Baseline spirometry measurements are expected to be missing for a small portion of patients due to patient refusal/inability, administration error, or spirometry measurements having insufficient quality. Data from the 12-month medical record review are expected to be missing for a small portion of patients (among those selected for follow-up) due to various problems accessing the medical record. Data from the 12-month patient survey are expected to be missing for a significant portion of patients due to patients not returning completed surveys.

Any missing data or data anomalies will be communicated to the site(s) for clarification/resolution. We will summarize the extent of missing data by intervention group. Patient demographics, other baseline characteristics, and available 12-month follow-up data will be compared between those with and without complete follow-up data, among those who were prospectively selected for follow-up, overall and by intervention group.

The primary analysis of the primary and secondary endpoints will be among those with complete follow-up (complete data for the relevant portions of both the chart review and follow-up survey).

For each Aim 3 endpoint that is collected via both medical record review and patient survey, sensitivity analyses will be conducted by imputing missing outcome data using different assumptions and applying the primary analysis method to the resulting data sets. Sensitivity analyses will include

1. Imputation of negative responses (i.e., responses indicating that the outcome has not occurred) for all missing patient survey responses, followed by analysis of all patients with medical record review data
2. Imputation of positive responses (i.e., responses indicating that the outcome has occurred) for all missing patient survey responses, followed by analysis of all patients with medical record review data; and
3. Multiple imputation of all missing outcome data using the observed outcomes and covariates, as described below, followed by analysis of all patients selected for follow-up.

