Multiple imputation of missing values in the baseline and 12-month follow-up data will be used to create 20 complete data sets. The set of patients included in each data set will be all of those selected for 12-month follow-up. The imputation method will be multivariate imputation by chained equations (MICE)⁶ as implemented in the R package 'mice'⁷.

Missing values of baseline spirometry FVC % predicted and FEV₁ % predicted will be imputed using linear regression models with the following predictors: age, gender, height, race, education, BMI, CAT score, asthma history, short-acting bronchodilator use, maintenance respiratory medication, and any follow-up outcomes for which baseline spirometry measurements will serve as predictors (selection of those predictors is described below). Predicted FVC and FEV₁ volumes will be calculated from the NHANES reference equations, allowing for calculation of the FVC, FEV₁, and FEV₁/FVC corresponding to the imputed % predicted values as needed.

For the purpose of organizing the imputation procedures, the 12-month follow-up outcomes will be grouped as follows:

- Pulmonary care outcomes:
 - Spirometry referral/completion
 - New diagnosis of COPD
 - New prescription for respiratory medication
 - Referral to pulmonologist or other respiratory specialist
 - Pulmonary rehab referral/completion
- Flu vaccination:
 - Flu shot recommended/ordered/administered
- Smoker-specific outcomes:
 - Counseling/recommendation for smoking cessation
 - Smoking cessation program referral/completion
 - New prescription for smoking cessation medication
 - Referral to a smoking quit line

Missing values of follow-up outcome variables, all of which will be binary (yes or no), will be imputed

using logistic regression models. For each outcome variable, the predictors will include, minimally, the following:

- All other variables from the medical record review and follow-up survey within the same group of outcomes. That is, medical record review data will be used to impute missing follow-up survey data, and follow-up survey data will be used to impute missing medical record data.
- Intervention group interacting with CAPTURE status. Intervention group must be included to avoid bias when using the imputed data to estimate the intervention effect. Interaction with CAPTURE status is included because the intervention effect is hypothesized to depend on the different recommendations associated with being classified as CAPTURE+ vs CAPTURE-.

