9.7 Multiple Testing

Two-sided p-values will be reported. When the primary analysis is repeated for each component of the primary endpoint (spirometry referral/completion, new COPD diagnosis, newly prescribed inhaled medication, referral to a respiratory specialist, and pulmonary rehabilitation referral/completion), a Bonferroni correction will be applied to that set of hypothesis tests. Otherwise, no adjustments for multiplicity will be made across analyses of primary and secondary endpoints and other exploratory analyses. Thus, corresponding p-values for these secondary and exploratory outcomes will be interpreted with caution. Confidence intervals will be provided to summarize treatment differences for efficacy end points.

10 Summary of Study Conduct Data

Descriptive summary statistics will be tabulated for baseline patient demographics and clinical characteristics as well as practice characteristics, separately by intervention group and overall. Intervention groups will be characterized as “Basic COPD Education” and “Basic COPD plus CAPTURE Education”. For pooled summaries, “All” will be used as the column heading. All tables will be annotated with the total population size relevant to that table, including any missing observations.

For continuous variables, sample means and standard deviations will be reported. P-values corresponding to two-sample t-tests¹ comparing mean differences between intervention groups will be reported. For categorical variables, number and percentages will be reported (excluding missing values). P-values corresponding to Pearson’s² chi squared statistic or Fisher’s³ Exact test for testing association between categorical predictors and intervention groups, as appropriate, will be given.

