We evaluated other scenarios including being able to increase enrollment to 150 patients per month with delays of two, four and six months and ending enrollment in January 2021 and March 2021.

Impact on Follow-up

The tables below present information on the initiation dates of the 12-month medical record abstraction by PBRN and the information on 12-month patient survey follow up as of March 25, 2020.

Table 8. 12-month Medical Record Abstraction (As of March 19, 2020)

| PBRN Site | Original ideal date of starting for 12- month medical records abstraction |
|-----------|---|
| A | 23MAR2020 |
| B | 30MAR2020 |
| C | Unknown |
| D | Unknown |
| E | 06APR2020 |
| F | No eligible patients until September 2020 |

Table 9. 12-month Patient Survey – COPD Foundation As of 3/25/2020

| | |
|---------------------------|-----------|
| Number Eligible | 380 |
| Phone Only | 118 |
| Email | 256 |
| Mail Only | 6 |
| Completed 12 Month Survey | 248 (65%) |
| Web | 84 |
| Phone | 134 |
| Mail | 30 |
| Mailed Surveys | 120 |
| Lost to Follow-Up | 20 |

Since all surveys are done by email, telephone call or mailings, there are no planned disruptions of the 12-month follow up patient surveys. All staff triggering email surveys, making telephone calls or preparing mailings are working from home.

Impact on Power

The goal of Aim 3 is to define the impact of CAPTURE information provided to clinicians in identifying and managing patients with respiratory symptoms (CAPTURE+) across a broad range of primary care settings. This Aim depends on the overall number of patients identified who are CAPTURE+, the number of practices enrolled as well as the ability to complete longitudinal follow-up.

Calculations were performed assuming 10 CAPTURE+/practice based on 67 total practices with > 1 CAPTURE+ patients (actual current state) taking into account loss of power due to variable cluster sizes. These data suggest that we are on track for having a well powered study for the primary analysis, even if additional data is difficult to obtain post-COVID crisis.

Table 10. Overall power to detect a difference in rate of meeting primary endpoint in CAPTURE group vs usual care, assuming 5% performance rate in usual care; 67 total practices; 10 CAPTURE+/practice

| Improvement over usual care | +7.5% | +10% | +15% | +25% | +50% |
|-----------------------------|-------|------|-------|-------|-------|
| ICC=0.05 | 0.76 | 0.92 | >0.99 | >0.99 | >0.99 |

| | | | | | |

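### SAP 9.5 fixes 20 imputed data sets with no seed and no Monte Carlo error check, so multiple-imputation p-values close to 0.05 or 0.01 can change side between seeds

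*SAP*

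**What the plan says.** SAP 9.5 plans imputation by chained equations in everyone chosen for the 12-month assessment: "Multiple imputation of missing values in the baseline and 12-month follow-up data will be used to create 20 complete data sets". SAP 11.2 repeats the primary and secondary efficacy analyses on these data sets and pools them by Rubin's rules with a t reference. Neither section gives a seed, a reason for 20 or a Monte Carlo error criterion.

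On the amount of missing data, SAP 9.5 is qualitative. For surveys: "Data from the 12-month patient survey are expected to be missing for a significant portion of patients". For charts: "Data from the 12-month medical record review are expected to be missing for a small portion of patients". The only count is Table 9 in SAP 13.1, a snapshot of 25 March 2020 with 380 eligible, 248 completed and 20 lost to follow-up.

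Two further statements set the stakes. Multiple imputation is not the main analysis: "The primary analysis of the primary and secondary endpoints will be among those with complete follow-up". For the five components of the composite, SAP 9.7 says that "a Bonferroni correction will be applied to that set of hypothesis tests", which means 0.05/5 = 0.01 per component.

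**The concern.** A pooled estimate from a finite number of imputations carries simulation noise. That noise grows with the fraction of missing information (FMI) and shrinks with m. The SAP expects substantial survey missingness, yet it fixes a small m and leaves the seed open.

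Multiple imputation is one of three sensitivity analyses in SAP 9.5. It is the only one that models the missing data and the only one that covers everyone selected for follow-up; the other two fill in all-negative or all-positive survey answers. If its p-value sits near a threshold, whether it appears to agree with the complete-case result may depend on the seed. An unstated seed also leaves open a choice that could be made after unblinding.

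**Working it through.** **Inputs from the documents.** m = 20 (SAP 9.5). Thresholds are 0.05 (SAP 11.1) and 0.05/5 = 0.01 (SAP 9.7). Survey counts come from Table 9 (SAP 13.1).

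**Table 9 reproduced.** 248/380 = 65.3%, as stated. Not completed: 380 − 248 = 132, or 34.7%. Lost to follow-up: 20/380 = 5.3%. Neither completed nor lost: 132 − 20 = 112.

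**From missing surveys to FMI (assumption).** The documents give no FMI. A patient whose chart already shows an event meets the composite whatever the survey says, so the FMI of the composite is below the missing share r. Take a complete chart, a chart-positive rate pc, and a survey-positive rate q among chart-negatives, and ignore clustering:

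FMI = 1 − (A + C)/(A + C/(1 − r)), with A = pc(1 − pc)(1 − q)² and C = (1 − pc)q(1 − q).

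Example with r = 0.35, pc = 0.10, q = 0.05: A = 0.0812, C = 0.0428, C/0.65 = 0.0658, so FMI = 1 − 0.1240/0.1470 = 0.16. Over pc 2–30% and q 2–10% it runs from 0.03 to 0.31. For an outcome recorded only in the survey it can approach r. The values used below are 0.15 for the composite and 0.31 for a survey-only component.

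**Monte Carlo error.** Scale so that the converged total variance is 1. Over seeds, the pooled estimate is normal around z with variance FMI/m. The between-imputation variance is B = FMI·χ²(m−1)/(m−1), the total is T = (1 − FMI) + (1 + 1/m)B, and p comes from a t distribution with Barnard–Rubin degrees of freedom (complete-data df 98; 1000 gives nearly the same).

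Seed-to-seed SD of the estimate, as a share of its standard error, is √(FMI/m). At m = 20 this is √(0.15/20) = 0.09 and √(0.31/20) = 0.12. At m = 100 it is 0.04 and 0.06.

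| Case | m = 20 | m = 100 |
|---|---|---|
| FMI 0.15, converged p 0.0375: central 95% range of p over seeds | 0.024–0.060 | 0.031–0.046 |
| FMI 0.15, mean share of seeds above 0.05 for converged p 0.03, 0.0375, 0.045 | 17% | 5.5% |
| FMI 0.31, mean share of seeds above 0.01 for converged p 0.006, 0.0075, 0.009 | 37% | 17% |
| FMI 0.15, threshold 0.05, averaged over trials: decision differs from converged | 2.3% | 1.0% |
| FMI 0.31, threshold 0.01, averaged over trials: decision differs from converged | 6% | 2.5% |
| FMI 0.15, threshold 0.05, no true effect, averaged over trials | 0.9% | 0.4% |

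Rows 2 and 3 are conditional on a p-value just under the threshold. Rows 4 and 5 average over trials with a true effect of z = 1.96 + 0.84 = 2.80, which is 80% power at 0.05. The same effect has power Φ(2.80 − 2.576) = 0.59 at 0.01. Under that effect only about 5% of trials have a converged p between 0.03 and 0.045. With a converged p of 0.001, crossing 0.05 is about 0% even at FMI 0.35.

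**The case against.** The strongest reply is that little hangs on this. The primary test is complete-case and uses no imputation. The two single-imputation analyses need no seed and cover everyone with a chart review, which should be nearly everyone. SAP 9.7 says secondary p-values will be read with caution and supplies confidence intervals, and no rule ties a conclusion to the multiple-imputation p-value. Every finite m leaves some seed dependence. All of this stands, and it makes the point minor.

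Three stronger readings are tempting, and the documents do not support them:

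- **That 35% of surveys are missing.** Table 9 is an interim count in which 112 of the 132 outstanding surveys were not listed as lost. The final share is not given and may be lower.
- **That p-values cross a threshold in 17% or 37% of runs.** Those figures hold only for converged p-values picked just under it. Averaged over trials, the rates are about 2% and 6%.
- **That the survey-only case certainly arises.** Tables 3 and 4 list specialist referral only under the survey. SAP 9.5 introduces the imputation analyses for endpoints collected from both sources, but then names specialist referral among the outcomes to impute, and SAP 11.2 carries no such restriction. Whether that component is analysed this way is ambiguous.

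What survives is narrower: near a threshold the result does move with the seed, nothing in the SAP detects or limits this, and the remedy is almost free.

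**Conclusion.** The point holds as a minor one. At m = 20, with no seed and no error check, a multiple-imputation p-value near 0.05 or 0.01 may fall on either side by simulation noise alone. Averaged over trials, this changes the decision in about 2% of cases for the composite and 6% for a survey-only component, against about 1% and 2.5% at m = 100. These figures rest on assumed FMIs of 0.15 and 0.31, a complete chart, an effect with 80% power at 0.05, and a survey-missing share near the March 2020 figure. A lower final share would shrink them.

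A reader might infer that the trial's main conclusion depends on the seed. It does not: the primary test involves no imputation, and results well clear of a threshold do not move across it.

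**What to change.** In SAP 9.5, replace 20 with at least 100 imputed data sets and pre-specify the random seed. Add that the Monte Carlo error of the pooled arm effect will be reported for the composite and each component. The seed makes the result reproducible and rules out choosing one later, but it does not make the result precise, so the larger m is needed as well.

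Setting m equal to the percentage of incomplete cases would not be enough. On the Table 9 figure that gives about 35, and at an FMI of 0.35 a converged p of 0.05 would still range over 0.028–0.089 between seeds, against 0.036–0.070 at m = 100.

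The same edit could state whether specialist referral is in the multiple-imputation analyses. The cost is a few lines of SAP text and computing time, with no effect on patients or data collection.

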Additional baseline predictors for imputing outcome variables will be included in the imputation procedure based on examination of study data that are blinded with respect to intervention group (pooled across intervention groups), assessing the association of each baseline variable with 1) whether the outcome data is missing, and 2) the outcome itself (among those with complete outcome data). To avoid including extraneous predictors, which may cause problems in fitting the logistic regression models and generating accurate imputations, we will use only baseline predictors that are associated with *both* the outcome missingness *and* the outcome itself, for at least one outcome in the group, based on p-values <0.01 from t tests¹ and chi-square tests². These additional baseline predictors will be selected separately for the medical record review variables and for the follow-up survey variables.

Based on the study data on March 21, 2023, from study sites for which all follow-up data have been collected (representing about 84% of the patients selected for follow-up), the additional baseline predictors for each outcome group would be the following:

| Outcome variable(s) | Predictors for medical record review | Predictors for follow-up survey |
|---------------------------------|--|---|
| Pulmonary care outcomes | PBRN Practice type Practice size (# clinicians) Patient enrollment date Education | Race Education Health insurance Smoking status FEV ₁ % predicted |
| Flu vaccination | PBRN Practice type Practice is a residency site Race Ethnicity Education | PBRN Age Race Education Health insurance Ever had flu shot |
| Smoker-specific outcomes | PBRN Practice type Practice is a residency site Practice size (# clinicians) Education | PBRN |

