11.1 Primary Efficacy Analysis

The primary efficacy analysis is restricted to CAPTURE+ participants, denoted in section 9.3 as population 1 (Primary Analysis Population). The primary analysis will be to compare the average cluster sample proportion (average proportion of CAPTURE+ patients per practice meeting composite endpoint) between intervention arms. Practices that do not identify any CAPTURE+ subjects will not contribute to this analysis. A two-sample test comparing average cluster sample proportions will be used that explicitly takes into account correlation between individuals treated within the same practice. A two-sided p-value < 0.05 will be considered statistically significant. This analysis corresponds to a generalized estimating equation (GEE)⁴ regression analysis with (1) individual-level binary composite outcome data, (2) CAPTURE intervention group as a covariate, (3) practice id used to identify correlated outcomes, (4) exchangeable correlation matrix that assumes similar correlation between all composite outcome results for patients within the same practice, and (5) an identity link function so that the coefficient parameter corresponding to CAPTURE intervention group represents a difference in outcome probability. The primary analysis would then correspond to a test for whether the CAPTURE intervention group parameter is non-zero.

Technical Details of the Primary Analysis:

This analysis is restricted to CAPTURE+ participants (Primary Analysis Population)

Let $\pi_{ij} = P(\text{Participant } j \text{ from Practice } i \text{ Meets the Primary Endpoint})$.

Let $CAPTURE_i = I(\text{Practice } i \text{ Received Basic COPD plus CAPTURE education intervention})$

Let PRACTICE take on values $i = 1, \dots, 100$ denoting the enrolled practices

For the primary analysis, the GEE model takes the form

$\pi_{ij} = \beta_0 + \beta_1 CAPTURE_i$, where binary outcomes from the same practice are assumed to follow a compound symmetry correlation structure.

R code for the Primary Analysis:

If the R dataset representing CAPTURE+ patients is called **final** and variables are

MetComp=1 if individual met primary (composite) outcome, 0 otherwise

CAPTURE=1 if individual was from a practice randomized to the Basic COPD plus CAPTURE education intervention, 0 otherwise

Practice is a variable with values $1, \dots, 100$ denoting the enrolled practices

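### The multiple-imputation models in SAP 9.5 carry no practice identifier or practice random effect, so the imputed-data analyses understate their standard errors modestly

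*SAP*

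**What the plan says.** **Imputation model (SAP 9.5).** The plan states: "The imputation method will be multivariate imputation by chained equations (MICE"), with 20 completed data sets. Missing binary outcomes are imputed "using logistic regression models. For each outcome variable, the predictors will include, minimally, the following". There are two compulsory sets of predictors. The first is "All other variables from the medical record review and follow-up survey within the same group of outcomes". The second is "Intervention group interacting with CAPTURE status".

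**Extra predictors (SAP 9.5).** Further variables pass through a screen: "we will use only baseline predictors that are associated with" both the missingness and the outcome, at p<0.01. The SAP tabulates what the screen selects on data of 21 March 2023, covering about 84% of the patients selected for follow-up:

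- Chart models, pulmonary-care outcomes: "PBRN Practice type Practice size (# clinicians) Patient enrollment date Education".
- Survey models, pulmonary-care outcomes: "Race Education Health insurance Smoking status" and FEV1 % predicted.
- The chart models for flu vaccination and for the smoker outcomes contain PBRN, practice type and residency status (the smoker model also has practice size). The survey models for these two groups contain PBRN.

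**Analysis model (SAP 11.1 and 11.2).** Each completed data set goes through a GEE with exchangeable correlation, with "practice id used to identify correlated outcomes". Results are pooled by Rubin's rules.

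**Role.** SAP 9.5 and Protocol 9.3.2 make the complete-case analysis primary. Multiple imputation is the third of three sensitivity analyses, and SAP 11.2 repeats it for the primary and secondary efficacy analyses.

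**The concern.** An imputation model should contain the structure that the analysis model will estimate. SAP 9.5 applies this principle to the intervention group, which it includes to avoid bias. It does not apply it to practice, the unit of randomization.

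Given the predictors, a single-level model draws values independently for two patients of the same practice. The completed data then look less clustered than the real data. The sandwich variance inside each data set is too small, and Rubin's between-imputation term does not restore the loss, because the draws do not vary by practice.

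The gap is widest where most imputation occurs. SAP 9.5 expects few missing charts but many missing surveys, and the pulmonary-care survey model is the one with no site-level variable. At stake is the calibration of the only planned analysis that includes every patient selected for follow-up. It is run across eight populations (SAP 9.3) and the subgroups of SAP 9.4.

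**Working it through.** **Inputs from the documents.** ICC 0.05, 0.10, 0.15; control rate 5%; two-sided 5% level; 5 CAPTURE+ patients per practice and 44 effective practices per arm (SAP 8.2). Ten CAPTURE+ per practice is the March 2020 memo's figure (SAP 13.1). Survey completion was 248 of 380 on 25 March 2020 (SAP Table 9), so 132/380 = 34.7% were not complete.

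**Assumptions not in the documents.** Chart missingness 5%; data missing completely at random; practice-size variation; chart-survey correlation within patient; chart and survey events equally frequent; no PBRN or practice covariates in the imputation.

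**Step 1: reproduce the plan's own clustered figure.** The SAP gives no standard error for the imputed analysis, so the nearest check is power at 5% vs 15%, ICC 0.10.

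Effective n per arm = 44 × 5 / (1 + 4 × 0.10) = 157.1. Null SE = √(2 × 0.10 × 0.90 / 157.1) = 0.0338. Alternative SE = √((0.05 × 0.95 + 0.15 × 0.85) / 157.1) = 0.0334. Power = Φ((0.10 − 1.96 × 0.0338) / 0.0334) = 0.843, against a stated 0.84. The other +7.5%, +10% and +15% cells of the SAP 8.2 power table, and of Table 10, agree within 2 points.

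**Step 2: simulate the imputation.** There were 100 practices, 5% vs 15%, the composite positive if chart or survey is positive, survey 35% missing, and 20 imputations. Each data set was analysed by the identity-link exchangeable GEE and pooled by Rubin's rules. The comparator adds a practice random intercept with its variance components fixed at their true values. The ratio is pooled SE divided by the empirical SD of the estimate.

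| CAPTURE+ per practice, ICC | Correlation: full data → no practice term | Ratio: full data | Ratio: no practice term | Ratio: random intercept | Gap |
|---|---|---|---|---|---|
| 5, 0.05 | 0.051 → 0.035 (−31%) | 0.977 | 0.969 | 0.998 | 0.029 |
| 5, 0.10 | 0.104 → 0.076 (−27%) | 0.990 | 0.961 | 0.998 | 0.037 |
| 5, 0.15 | 0.150 → 0.114 (−24%) | 0.969 | 0.927 | 0.972 | 0.045 |
| 10, 0.10 | 0.102 → 0.074 (−27%) | 0.963 | 0.910 | 0.978 | 0.068 |

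The gap (random intercept minus no practice term) isolates the omission, at about 3-7 points. The random intercept brings the correlation back to 0.051, 0.104, 0.149 and 0.101. Without a practice term the mean estimates are 0.0985-0.0994 against a true 0.10, so bias is negligible. A second simulation, with no missing charts, gave a correlation fall of 22-23% and pooled SEs 2-7% low, against 0-3% low with full data.

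**Step 3: check by hand.** With equal practice sizes the SE scales with √(1 + (m − 1) × ICC).

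- m = 5: √(1.140/1.204) = 0.973; √(1.304/1.416) = 0.960; √(1.456/1.600) = 0.954.
- m = 10: √(1.666/1.918) = 0.932.

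These are shortfalls of 2.7%, 4.0%, 4.6% and 6.8%, in line with the gaps above.

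**Step 4: type I error.** If the SE is r times the true SD, the rejection rate is 2Φ(−1.96r). The no-practice ratios give 5.8%, 6.0%, 6.9% and 7.5%. The full-data ratios give 5.6%, 5.2%, 5.8% and 5.9%. Direct simulation under the null agrees. With 10 per practice and mean ICC 0.06, 0.12 and 0.18 (2,500 trials each), rejection was 6.0%, 6.4% and 7.3%, against 5.3-5.7% with full data. The simulation without missing charts gave 5.9-7.7% against 5.0-6.0%.

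**The case against.** **The models are not blind to site.** This stands. A reader might infer that no imputation model knows anything about where a patient was treated. The SAP 9.5 table shows otherwise: five of its six predictor lists contain PBRN, and every chart list adds practice descriptors. The simulations left these out, which somewhat overstates dilution for imputed chart values. It does not help the pulmonary-care survey model.

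**Same-patient chart outcomes carry some of the clustering.** This also stands. They are predictors, and a positive chart component settles the composite whatever the survey would have said. The correlation is diluted, not removed. A larger effect appears if the outcome is taken from the survey alone, but that does not describe the composite. Among its five components, only specialist referral is listed solely in the survey table (SAP Tables 3 and 4).

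**Part of the shortfall belongs to the GEE.** Sandwich SEs are already 1-4% low with complete data. Monte Carlo error is about 2-3% on the ratios and about 0.5 points on the rejection rates, so the smallest effects are near noise. The direction is the same in every setting.

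**The 35% is an interim count.** Only 20 of the 380 were then classed as lost to follow-up, so final missingness may be lower.

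**The word *minimally* leaves room for more predictors.** This carries little weight. Additions come through the screen, which selects individual baseline variables, and its tabulated result contains no practice identifier.

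**The SAP limits predictors to avoid fitting problems.** This is a fair caution for sparse outcomes, and it bears on how the fix is built.

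**Conclusion.** The concern holds at modest size. Followed as written, the multiple-imputation analyses treat outcomes as less clustered by practice than they are. For the composite, the within-practice correlation drops by roughly 20-30%, omitting practice accounts for a standard-error shortfall of about 2-7%, and type I error is about 6-7.5% rather than 5-6% with full data. The effect grows with practice size and with the amount of missing survey data. These figures rest on the assumptions listed in the working, chiefly 35% survey missingness, and on a comparator that knew the true variance components.

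Two stronger readings are not supported. A reader might infer that the trial's main result is compromised. It is not: the primary test is the complete-case GEE, and the two single-value imputations, which cover everyone with chart data, do not use these models. A reader might also infer a biased treatment effect, but the point estimates stay essentially unbiased, so multiple imputation still shows whether the estimate moves when non-responders are included. Its confidence intervals and p-values are what come out slightly optimistic. This is a worthwhile and inexpensive improvement to a sensitivity analysis.

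**What to change.** In SAP 9.5, specify that the follow-up outcomes are imputed with a practice random intercept (two-level chained equations). The alternative is to resample whole practices by bootstrap and impute within each resample. In either case, report the within-practice correlation of the composite before and after imputation, so that any remaining dilution is visible. Adding PBRN to every outcome model is optional: the primary GEE has no PBRN term, so compatibility does not require it.

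The cost is a few sentences in the SAP and more computing; no new data are needed. The downside is that two-level logistic models may be unstable for rare outcomes with 5 to 10 patients per practice. The SAP should name a simplified two-level model as the fallback for those.
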